- A compelling rationale for proposed exclusion of any sex/gender or racial/ethnic group;
- The proposed dates of enrollment (beginning and end);
- The proposed sample composition of subjects.

You may reference grant application/sponsor's relevant protocol pages and attach as an appendix using the below attachment button, however, a summary paragraph must be provided in the text box below.

It is anticipated that 990 CKD-5D patients will be enrolled. The study population will include men and women age 21 years and over from various ethnic backgrounds. The enrollment will be done between January 2015 and January 202119.

TARGETED/PLANNED ENROLLMENT: Number of Subjects

Ethnic Category Sex/Gender

Females Males Total

Hispanic or Latino 15 15 30

Not Hispanic or Latino 480 480 960

Ethnic Category: Total of All Subjects * 495 495 990

Racial Categories

American Indian/Alaska Native

Asian 3 3 6

Native Hawaiian or Other Pacific Islander

Black or African American 225 225 450

White 267 267 534

Racial Categories: Total of All Subjects * 495 495 990

Inclusion Criteria:

- Aged 21 years or older;
- Chronic maintenance dialysis of at least 3 months' duration;
- Mental competence;
- Willingness to participate in the study;
- Normal corrected serum calcium.
- Low bone densityOsteoporosis by DXA scan in any site. (T-score = -1-2.5 for men over age 50 or postmenopausal women, or Z-score = --12.5 for all others).

Exclusion criteria:

- Pregnancy or Breast Feeding;
- Incarceration
- Systemic illnesses or organ diseases that may affect bone (except type 1 or type 2 diabetes mellitus);
- Clinical condition that may limit study participation (e.g., unstable angina, respiratory distress, infections).
- Chronic alcoholism and/or drug addiction;
- Known Paget 's disease of bone;
- Prior external beam or implant radiation therapy involving the skeleton, only if randomized to the Teriparatide treatment
- Participation in a study of an investigational drug during the past 90 days;
- Planning to move out of the area within 1 year of the study;
- Scheduled for renal transplantation
- BMD T-score of the radius less than -3.5 by DXA. (if randomized to teriparatide to avoid the known potential negative effects of teriparatide treatment on BMD of the radius)
- Current treatment with medicines containing digoxin;
- More than 3 CT scans in the prior 12 months (to avoid excessive radiation exposure);
- Planned or anticipated oral surgery within the next 12 24 months;

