Treatment Protocol for Teriparatide: Patients with low bone turnover will receive a starting dose of 20 µg teriparatide per day via subcutaneous injections along with 30 mg of cinacalcet p.o. daily in the evening will be added after two weeks if PTH is greater than 200 pg/mL at the first biweekly lab draw. Teriparatide treatment alone in patients with histologically proven low turnover bone disease did not result in an increase in bone formation markers.²⁵ Concomitant treatment with cinacalcet is needed in these patients when intact PTH is above 200 pg/mL. To monitor control of PTH and serum calcium levels we will measure them initially one week +/- 3 days after treatment then at the biweekly monitoring visits at the CCTS and quarterly thereafter. Teriparatide dosage will be adjusted according to changes in serum calcium. If serum calcium is between 10.2 and 11 mg/dL, frequency of injection will be reduced to 5 of 7 days per week (non-injection days should not be consecutive and blood draws for serum calcium should be the morning after an injection day). A follow-up visit with serum calcium check will be scheduled in two weeks +/- 3 days. If at that time calcium levels are still between 10.2 and 11, patients will remain with injections on 5 of 7 days per week. If calcium levels return to below 10.2 mg/dL, daily injections will be reinstated and quarterly calcium checks will be performed. If serum calcium is greater than 11.0 mg/dL, treatment will be withheld for two weeks at which time serum calcium will be rechecked. If it is between 10.2 and 11.0 mg/dL we will reinstitute treatment at the reduced frequency of 5 of 7 days per week. If calcium remains above 11.0 mg/dL, patients will be referred to their primary nephrologist for workup of their hypercalcemia and excluded from further participation in the study.

To assess response or compliance to teriparatide, BSAP (see Table 2) will be measured bi-weekly until steady-state and quarterly thereafter. If results do not increase at least 8% (largest inter-assay error of this marker) the study coordinators will carefully review with the patients the technique of injections and possible compliance lapses. There are no known critical levels indicating undesirably high response without concomitant hypercalcemia. Patients, and if needed a caregiver, will be trained in the subcutaneous administration of teriparatide according to the manufacturer's guidelines.

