Table 2. Detail of Blood Draws for Monitoring Safety and Compliance and Secondary Endpoint Serum Biochemical Parameters
Teriparatide

Treatment Group Base-line Bi-weekly visits until steady state Q1 Visit Q2 Visit Q3 Visit 1 Year 15 mo 18mo 21mo 2 yr
or Safety: Serum Calcium & PTH X X X X X X X X X X X X

For Compliance: BSAP X X X X X X X X X X

Secondary Endpoints: FGF23, P1NP, Sclerostin, DKK-1 & PTH Ratio X X X X X

Alendronate

Treatment Group Base-line Monthly visits until steady state Q1 Visit Q2 Visit Q3 Visit 1 Year 15 mo 18mo 21mo 2yr

For Safety and Compliance: BSAP X X X X X X X X X X

Secondary Endpoints: Serum Calcium, PTH & PTH Ratio, FGF23, P1NP, Sclerostin, DKK-1 X X X X X

Standard of Care Controls Base-line Q2 Visit 1 Year 15mo 18mo 21mo 2 yr

Secondary Endpoints: All of the above Serum Biochemical Parameters X X X X X

Cinacalcet will be adjusted in 30 mg steps up to a maximum daily dose of 180 mg if needed to keep intact PTH at levels less than 200 pg/mL. If by six weeks, this fails to achieve PTH levels less than 200 pg/mL, patients will be excluded from further study participation. In the rare case where PTH level maintenance requires cinacalcet doses that induce serum calcium levels below 8.5 mg/dL, treatment will cease for two weeks after which calcium will be re-measured. At two weeks if calcium remains below 8.5 mg/dL, patients will be excluded from further participation in the study. If calcium is normalized, cinacalcet will be reinstated at half of the prior dose. Calcium will be checked again at the next monitoring visit. If at any measurement point PTH levels are less than 60 pg/mL cinacalcet will be withheld and reinstated if levels are again above 200 pg/mL.

Treatment Protocol for Alendronate: Patients with normal or high bone turnover will receive a starting dose of 35 mg alendronate p.o. once per week. Patients will be carefully instructed to follow the manufacturer's recommendations for administration. Serum calcium will be rechecked 1 week +/- 3 days after starting therapy. Dosage will be adjusted according to changes in the bone turnover marker

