Teriparatide for patients with low bone turnover: Patients with increased baseline risk of osteosarcoma will be excluded from this study (Paget's disease of bone, pediatric populations and young adults with open epiphyses, or prior external beam or implant radiation therapy). Our inclusion/exclusion criteria eliminate all of these patients. There are no direct contraindications given for CKD patients given in the package inserts and the safety web page. However, because bone loss with CKD-5D is not specifically addressed in the indications, we have obtained an IND (Investigational New Drug) from the FDA.

If during the monthly monitoring calls/visits or quarterly visits patients complain of new onset adverse reactions such as arthralgia, pain, nausea, dizziness or leg cramps, the patients will be counseled regarding standard treatment measures. Follow-up contact will be made in one week and if symptoms persist, treatment will be discontinued until the next regularly scheduled quarterly monitoring visit. Follow-up communication will occur within 1 week +/- 3 days and if problems persist despite discontinuation, patients will be referred to his/her primary care provider.

If patients complain of injection site reactions, they will be counseled regarding their injection technique and follow-up contact will be made in one week +/- 3 days. If reactions persist, treatment will be discontinued until next regularly scheduled quarterly monitoring visit. If problems persist despite discontinuation, patients will be referred to his/her primary care provider and their participation in the study will end.

In the rare case where PTH level maintenance requires cinacalcet doses that induce serum calcium levels below 8.5 mg/dL, treatment will cease and patients will be excluded from further participation in the study.

Alendronate for patients with normal or high bone turnover: Our inclusion/exclusion criteria cover all of the above-mentioned contraindications. To be safe, we have obtained an IND from the FDA.

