If during the monthly monitoring calls/visits or quarterly visits patients complain of new onset gastrointestinal problems, the patients will be counseled regarding the drug intake technique, and standard treatment will be given including over the counter antacids or proton pump inhibitors. Follow-up contact will be made in one week +/- 3 days and if symptoms persist, study treatment will be discontinued until the next regularly scheduled quarterly monitoring visit. If symptoms have disappeared at this visit, treatment will be reinstated and monitoring will continue. If symptoms respond within 1 week to antacid management, study treatment will be reinstated. Thereafter, if patients complain of new onset symptoms at the next monthly monitoring call or call themselves earlier, treatment will be discontinued and study participation will end.

If patients complain of new onset musculoskeletal pain, they will be given over-the-counter pain medication and follow-up contact will be made in one week +/- 3 days. If pain persists, study treatment will be discontinued until next regularly scheduled quarterly monitoring visit. Follow-up communication will occur within 1 week +/- 3 days and if problems persist despite discontinuation, patients will be referred to his/her primary care provider.

Blood draws. Compression after blood drawing will reduce the incidence of bruising. All blood draws will be performed with the patient in the sitting position to avoid falls after fainting.

Confidentiality. All patient information will be coded, and the master data kept under lock and key in the study coordinators' office. Access to the codes will be available only to the PI, the data manager/analyst and study coordinators.

Benefit vs. Risk: Describe potential benefits to the subject(s); include potential benefits to society and/or general knowledge to be gained. Describe why the risks to subjects are reasonable in relation to the anticipated benefit(s) to subjects and in relation to the importance of the knowledge that may reasonably be expected to result. If you are using vulnerable subjects (e.g., impaired consent capacity, pregnant women, etc...), justify their inclusion by describing the potential benefits of the research in comparison to the subjects' vulnerability and the risks to them. For information about inclusion of certain vulnerable populations, see the IRB/ORI Standard Operating Procedure for Protection of Vulnerable Subjects [C3.0100] [[PDF](#)].

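### Five rules end study participation rather than study drug alone, and all apply only to treated patients, so one-year hip BMD can be lost selectively; the size and direction of any bias are unknown.

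*Combined protocol and SAP*

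**What the plan says.** **Teriparatide group, rules that end participation**

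- *High calcium* (Research Procedures, Treatment Protocol for Teriparatide). If calcium is still above 11.0 mg/dL after two weeks off drug, "patients will be referred to their primary nephrologist for workup of their hypercalcemia and excluded from further participation in the study".
- *PTH* (Research Procedures, cinacalcet adjustment after Table 2). "If by six weeks, this fails to achieve PTH levels less than 200 pg/mL, patients will be excluded from further study participation".
- *Low calcium on cinacalcet*. This is written twice. Research Procedures has a two-week pause and then: "At two weeks if calcium remains below 8.5 mg/dL, patients will be excluded from further participation in the study". Safety Precautions has no recheck: "treatment will cease and patients will be excluded from further participation in the study".
- *Injection-site reactions* (Safety Precautions). If problems continue even after the drug has been stopped, "patients will be referred to his/her primary care provider and their participation in the study will end".

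**Alendronate group**

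- *Gastrointestinal symptoms that return after a first episode was managed* (Safety Precautions): "treatment will be discontinued and study participation will end".

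**Controls.** Table 2 lists their visits. No passage gives a reason to remove them.

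**Contrast within the plan.** Elsewhere the drug is stopped without a statement that participation ends. For musculoskeletal pain on alendronate: "If pain persists, study treatment will be discontinued until next regularly scheduled quarterly monitoring visit". The low-BSAP rule works the same way.

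**Exclusions that depend on allocation** (Study Population, Exclusion criteria). The radius T-score criterion is worded to apply if the patient is randomised to teriparatide. The radiation criterion reads "Prior external beam or implant radiation therapy involving the skeleton, only if randomized to the Teriparatide treatment".

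**Endpoint and schedule.** The primary endpoint compares change in total hip QCT BMD between treatment and control, assessed at one year (Research Procedures, Primary Endpoint). QCT is at baseline, 6 months and 12 months, and later (Objectives; Study Design).

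**The concern.** Each rule responds to tolerance or to a laboratory result that occurs only, or is acted on only, under study treatment. If leavers are not scanned, the one-year comparison could set treated patients who tolerated the drug and met the PTH and calcium limits against controls who faced no such filter. Randomisation would no longer protect that comparison. A scan that was never taken cannot be recovered at analysis.

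The plan distinguishes stopping drug from leaving the study, so the exits are not simply loose wording. No available passage keeps the removed patients for the 6- and 12-month scans, defines an analysis set, or gives a missing-data method. The monitoring section reviews drop-out, but counting leavers does not replace their data. MDCT follows the same schedule, so the calcification endpoint is exposed in the same way.

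**Working it through.** **1. Count of rules.** Teriparatide 4 (low calcium counted once despite its two versions), alendronate 1, controls 0.

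**2. Who each rule reaches.** Cinacalcet is added only if PTH exceeds 200 pg/mL at the first biweekly draw. The PTH rule judges whether cinacalcet titration works. On the natural reading, the PTH and low-calcium rules therefore reach only the patients given cinacalcet. The high-calcium, injection-site and gastrointestinal rules each need the problem to persist or recur.

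**3. What is lost.** An exit at week 6 falls before the 6-month QCT, so only baseline remains. An exit between months 6 and 12 leaves the 6-month scan but can lose the 12-month one.

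**4. What the documents say about frequency.**

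- Low calcium on cinacalcet is called rare.
- Persistent hypercalcemia is called rare, in osteoporosis trial patients (Potential Risks).
- Gastrointestinal side effects were 13% v 11% over 12 weeks in post-menopausal women; the rule needs recurrence.
- For PTH there are only the six pilot patients in Background. If none failed, the exact 95% upper limit is 1 - 0.025^(1/6) = 0.459, or 46%, too wide to help.

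**5. Scale, on assumed inputs.** The plan gives no figure to reproduce. Let n be the number randomised per group, p the share removed from the treated group, and g the stayer-minus-leaver gap in SD units. If leavers contribute nothing:

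- bias = p × g
- SE = sqrt(1/(n(1-p)) + 1/n)
- two-sided 5% normal test, no true effect, unit SD.

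| p | g | bias (SD) | SE, n=40 | SE, n=100 | false-positive, n=40 | false-positive, n=100 |
|---|---|---|---|---|---|---|
| 5% | 0.25 | 0.0125 | 0.2265 | 0.1433 | 5.0% | 5.1% |
| 10% | 0.5 | 0.05 | 0.2297 | 0.1453 | 5.5% | 6.4% |
| 20% | 1 | 0.20 | 0.2372 | 0.1500 | 13.5% | 26.6% |

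The false-positive rates are the same for either sign of g. A 10% rate needs bias/SE = 0.652. At n=100 that is a bias of about 0.09-0.10 SD, for example p=10% with g=0.95, or p=20% with g=0.49. At n=40 it is about 0.15 SD.

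If the gap runs against the drug, power for an assumed 0.5 SD effect at n=100 is 93%, 87% and 52% in the three rows, compared with 94%, 93% and 92% with no gap.

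For the alendronate rule alone, assuming p of 1-13% and g of 0.25-1 SD, the bias is 0.0025-0.13 SD and the false-positive rate 5.0-14.4% (upper end at n=100).

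**6. Radius exclusion.** If a share q is excluded from one group only, and radius T-score has correlation r with hip BMD change, the shift is r × φ(z_q)/(1-q). With assumed q=2%, r=0.1: 0.1 × 0.049 = 0.005 SD. With q=15%, r=0.3: 0.3 × 0.274 = 0.08 SD. The direction is unknown.

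**The case against.** The strongest reply is that exposure is inferred from a count of rules, not from rates. Two of the four teriparatide rules reach only patients given cinacalcet. Low calcium and persistent hypercalcemia are called rare, the latter in trial patients who were not the dialysis population studied here. The injection-site rule applies only when the problem outlasts a drug stop. With small shares the calculated effect is negligible. All of this stands. A reader might infer that the low-turnover arm will lose materially more data; the documents support only that it has more rules.

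Second, p × g assumes a completers-only comparison, which the plan nowhere prescribes. A patient who leaves after month 6 has a QCT that a longitudinal model could use, so for that patient the formula is a worst case. It applies in full to week-6 exits. Allocation that adapts to group completion rates may even out numbers, but it does not restore comparability.

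Third, a reader might infer bias in favour of the drug, since the plan itself holds that teriparatide alone did not raise formation markers in low-turnover patients and that cinacalcet is needed when PTH is high. That is an argument about one rule. The others may act the opposite way, and no data settle the net direction.

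Fourth, the prior-radiation wording might be read as a flat contradiction. It is softer than that: the broader statement in Safety Precautions sits under the teriparatide heading and defers to the eligibility criteria.

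Finally, restricting attention to patients with controlled PTH is a defensible question for a phase II proof of concept. It can be asked as a sensitivity analysis without giving up the scans.

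**Conclusion.** The concern holds as a design weakness that should be fixed, with medium confidence. As written, five treatment-only rules end participation, no counterpart exists for controls, and no available text keeps leavers for the one-year scan. Following the plan can therefore remove primary outcome data by group.

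How much this matters is not known. Share removed, gap and group size are all assumed above; the range runs from negligible (5.0-5.1% false positives) to serious (13.5-26.6%), and no passage supports or excludes the serious end. The documents do not support saying that the result will be biased, in which direction, or that the low-turnover arm will in fact lose more.

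The attachments named under Study Design and Research Procedures, the consent forms and some pages were not available. A continued-follow-up rule there would answer most of this point.

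**What to change.** **(a) Separate stopping drug from leaving the study.** Leave every drug-stopping rule unchanged. State that meeting one ends study drug only, and that consenting patients stay for the 6- and 12-month QCT and MDCT already scheduled. Analyse all randomised patients in their assigned group, with completers as a sensitivity analysis, and report exits by rule and group. With everyone scanned, these rules remove no one-year data.

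The cost is protocol, analysis and consent wording, some CT scans in patients off drug, and some dilution. For an assumed 0.5 SD effect at 100 per group, with patients off drug gaining nothing, the effect becomes 0.5(1-p) and SE = sqrt(2/100). Compared with completers and no gap, power moves from 94% to 92% with 5% off drug, 93% to 89% with 10%, and 92% to 81% with 20%.

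**(b) Take the radius criterion out of the post-allocation step.** The radius is already measured by DXA at screening. Assess the criterion before randomisation and apply it to both low-turnover groups. The cost is the loss of some otherwise eligible controls (assumed 2-15%).

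**(c) Separately, reconcile the text.** Research Procedures and Safety Precautions differ on whether low calcium is rechecked before exclusion. The exclusion criteria and Safety Precautions should be clarified against each other on prior radiation; if it remains specific to teriparatide, handle it as in (b). This review takes no view on which version is right.

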BSAP from blood drawn at monthly monitoring visits for the first 3 months, thereafter at quarterly monitoring visits. BSAP is expected to go down, but to avoid over-suppression, will not be allowed to go below the low normal range of the assay, as is done clinically. Our data show that mid/normal ranges of these markers in CKD-5D patients indicate low turnover^{48, 49} If this safety threshold is crossed, treatment will be stopped until values are back above the threshold at a regularly scheduled monitoring visit. Once demonstrably back within safety threshold, treatment will be reinstated at half of the initial dose (35 mgs every other week). If BSAP does not go down at least 8% over a one month period, treatment doses will be doubled to 70 mgs per week. If they still remain high, study coordinators will carefully review with the patients the mode of drug intake and possible compliance lapses.

Primary Endpoint At one year after baseline, we will assess bone mass using QCT BMD measurements of the total hip and compare 1 and 2 year changes in bone mass between the treatment and control groups. Total hip will be used as the primary endpoint site because in our prior funding period we showed that changes at the total hip in QCT BMD are more pronounced than at the spine⁶. The Secondary endpoint will be differences between the treatment and control groups in changes in coronary artery calcifications by MDCT. This will be relevant regardless of bone effects.

Other secondary endpoints tracked at baseline, 6 months, and 1 year, 18 and 24 months will include serum biochemical markers of bone activity; FGF 23, BSAP, TRAP5b, P1NP, Sclerostin, and DKK1.

Additionally we will record 1) Change in QCT BMD of the spine to compare with the hip) 2) Changes in DXA BMD of the hip and spine (to determine whether the more commonly available DXA results are equivalent to QCT and 3) Changes in aortic and heart valve calcification (to compare with the coronary artery calcifications).^{50,51} 4) Whole body composition (%fat vs %lean) as it relates to survival in CKD-5D patients.

Attachments

Attach Type	File Name
ResearchProcedures	figure 3 7.22.2019 pdf.pdf

Data Collection: List the data or attach a list of the data to be collected about or from each subject (e.g. interview script, survey tool, data collection form for existing data).

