Metabolic side effects have included reductions in serum calcium and phosphorus levels as a result of the inhibition of bone resorption. These reductions generally have been mild, asymptomatic, and transient. Musculoskeletal side effects have included bone, muscle or joint pain in approximately 4% of patients. Localized osteonecrosis of the jaw generally associated with tooth extraction and/or local infection has been reported rarely and is likely associated with over-suppression of bone turnover. Also, low-energy femoral shaft and sub-trochanteric insufficiency fractures have been reported in post-marketing experience after long-term use of alendronate (>5 years). Again, over-suppression of turnover is a likely cause.

Teriparatide is indicated: a) for the treatment of postmenopausal women with low bone densityosteoporosis at high risk for fracture, b) to increase bone mass in men with primary or hypogonadal low bone densityosteoporosis at high risk for fracture, and c) for the treatment of men and women with bone lossosteoporosis associated with sustained, systemic glucocorticoid therapy (daily dosage equivalent to 5 mg or greater of prednisone) at high risk for fracture. The risks associated with using teriparatide for treatment of osteoporosis in men and women was assessed in two randomized double blind placebo controlled trials of 1,382 patients, mean age 67 years.⁷¹ All-cause mortality, incidence of serious adverse events and discontinuation due to adverse events, were similar or even lower in the teriparatide group. Adverse reactions that were higher in the teriparatide group include: arthralgia, pain, and nausea. Other adverse reactions include dizziness, leg cramps, and injection site reactions. Persistent hypercalcemia is a rare occurrence in these patients. Teriparatide is not used in patients with hypercalcemic disorders and Paget's disease; these are inclusion/exclusion criteria for this study.

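### The alendronate BSAP stop and restart limit is set at low-normal, yet the next sentence says mid-normal values already indicate low turnover; the two are not reconciled

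*Combined protocol and SAP*

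**What the plan says.** The relevant text is the Treatment Protocol for Alendronate in Research Procedures. Dose is adjusted on "BSAP from blood drawn at monthly monitoring visits for the first 3 months, thereafter at quarterly monitoring visits". BSAP is expected to fall on treatment but, "to avoid over-suppression, will not be allowed to go below the low normal range of the assay, as is done clinically". The sentence that follows gives the investigators' own evidence in dialysis patients: "Our data show that mid/normal ranges of these markers in CKD-5D patients indicate low turnover". The plan then calls the low-normal limit a safety threshold. If it is crossed, "treatment will be stopped until values are back above the threshold at a regularly scheduled monitoring visit", and restart is at half the initial dose. Dose increase is governed separately: "If BSAP does not go down at least 8% over a one month period, treatment doses will be doubled to 70 mgs per week".

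Three other places bear on this:

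- Treatment Protocols (Normal or High Turnover Groups) randomises only patients with normal or high turnover to alendronate or control.
- Table 2 lists BSAP as the only safety and compliance marker for the alendronate group.
- Potential Risks links over-suppressed turnover to osteonecrosis of the jaw. On femoral shaft and sub-trochanteric fractures after long-term use it says: "Again, over-suppression of turnover is a likely cause".

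**The concern.** The threshold sentence and the evidence sentence stand side by side and point in different directions. The limit rests on ordinary clinical practice with the assay's normal range. The evidence sentence says that this range means something different in dialysis patients, because values in the middle of it already go with low turnover. If that is so, a patient can be in low turnover by the plan's own statement while the safety rule has nothing to say.

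This matters on the plan's own terms. The trial's premise, set out in Background, is that treatment should follow turnover status and that undesirable effects are seen when it does not. Alendronate is given to reduce resorption in patients whose turnover is not low. The Benefit vs. Risk section relies on careful monitoring to control the risks, and the BSAP limit is the only rule in the alendronate group that is aimed at over-suppression.

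**Working it through.** The plan gives no figure to reproduce. The check is an ordering of levels on one scale, followed by applying each rule to the band between them.

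**Inputs.** Let *L* be the low-normal BSAP limit and *M* the mid-normal level. Both come from Treatment Protocol for Alendronate, and neither has a numeric value anywhere in the documents. Let *B* be a patient's current BSAP and *B₀* the value one month before.

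**Ordering.** Low-normal is below mid-normal by definition, so *L* < *M*. BSAP is expected to fall, so a patient who starts above *M* and later reaches *L* passes through the band *L* ≤ *B* < *M* on the way. A patient may also start inside the band. Turnover at entry is classified by PTH, PTH ratio and TRAP-5b (Research Procedures), not by BSAP.

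**Each rule inside the band *L* ≤ *B* < *M*:**

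- Stop rule: triggers only if *B* < *L*. It does not trigger.
- Restart rule, after an earlier stop: triggers once *B* is back above *L*. It can trigger, and treatment resumes at half the initial dose in a range that the plan labels low turnover.
- Doubling rule: triggers if BSAP has fallen by less than 8% in a month, that is, if *B* > (1 − 0.08) × *B₀* = 0.92 × *B₀*. The condition depends only on the ratio *B*/*B₀*. It holds as readily inside the band as above it, because no absolute level appears in it.

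**Wording.** The evidence sentence can be read as referring to mid-normal values or to mid and normal values generally. On the second reading the band is wider. Neither reading removes it.

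**Search for a resolving rule.** Table 2 gives no second safety marker for this group. The text adds a serum calcium check about one week after starting, which does not address turnover. Nothing says that the markers used at entry are rechecked to detect a move into low turnover on treatment. No other section gives a different BSAP limit.

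**Timing.** After month 3 the draws are quarterly, so even a crossing of *L* can go unseen for up to about three months.

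**Size.** The width *M* − *L* and the share of patients in the band need the assay reference range, a BSAP cut-off for low turnover and the distribution of BSAP on treatment. The documents give none of these, so no estimate is offered.

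**The case against.** The strongest defence is that over-suppression and low turnover need not be the same thing. The plan never equates them. If over-suppression means something more extreme, a stop limit below the low-turnover level is not a strict logical contradiction. The evidence sentence might even be meant to explain why going below normal would be excessive in these patients. This stands as a possible reading, but the plan defines no separate level for over-suppression and does not explain how the two sentences relate. A site applying the rule cannot tell which was meant.

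Second, BSAP is not how the plan classifies turnover at entry, the evidence sentence is loosely worded and refers to markers in the plural, and the sources that it cites cannot be checked here. This limits what can be said about clinical consequence. It does not explain why the sentence stands next to the BSAP limit.

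Third, the sentence after the doubling rule speaks of values that remain high, which suggests that the authors had high BSAP in mind. The trigger as written does not say so.

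Fourth, other safeguards exist: monthly adverse-event contact, half-dose restart and DSMB oversight. The plan ties the femoral fractures to more than 5 years of use, against at most two years here. It describes jaw osteonecrosis as rare and generally linked to tooth extraction or local infection, and the exclusion criteria cover planned oral surgery. All of this is fair, and it tempers the clinical stakes. None of it reconciles the two sentences.

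**Conclusion.** The inconsistency is real and should be corrected before the rule is relied on. Followed as written, the protocol can keep patients on alendronate, restart them, or double their dose at BSAP values that its own evidence sentence associates with low turnover. The conclusion rests on two assumptions: that low-normal lies below mid-normal, and that the evidence sentence covers BSAP, the only marker named in the rule. Its size is unknown.

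A reader might infer three stronger things that the documents do not support:

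- That the rule acts only once harm has occurred. The plan does not say that mid-normal BSAP is over-suppression or that it causes fracture or osteonecrosis.
- That the treatment-control comparison is compromised. Patients are assigned to an arm on baseline turnover and randomised within it, so a later fall in turnover on alendronate is an effect of treatment and does not bias the contrast in hip BMD.
- That about half of the normal range is left uncovered. No assay range is given, so no fraction can be stated.

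**What to change.** The investigators should reconcile the threshold sentence with the evidence sentence, and say in the text how over-suppression relates to low turnover as measured by BSAP. They should then state the resulting BSAP limit as a number for the assay used and make the stop, restart and dose-doubling rules consistent with it, including whether the doubling rule depends on the absolute BSAP level. Which limit or rule is right is a clinical decision for them, and none is proposed here.

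The cost is a protocol wording change. BSAP is already drawn at every alendronate monitoring visit, so no extra samples or visits are needed.
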